5.4.7 Adverse Events Reporting Timeline

1. Serious and unexpected, suspected adverse reactions to the study drug: The serious and unexpected, suspected adverse reaction will be reported to the DCC and overall study PI as soon as possible, but no later than 15 calendar days after the site Investigator receives the respective information.

All reviewing IRBs will also be notified of serious and unexpected, suspected adverse reactions in accordance with the respective policies and procedures of the IRBs. The DSMB and all Investigators (i.e., study site principal investigators) will also be promptly notified of serious and unexpected, suspected adverse reactions.

2. Unexpected life-threatening or fatal, suspected adverse reactions associated with the use of the study drug: The unexpected, life-threatening or fatal, suspected adverse reaction will be reported to the DCC, overall PI, and DSMB as soon as possible, but no later than 2 working days after the site Investigator receives the respective information.

All reviewing IRBs will also be notified of unexpected, life-threatening or fatal, suspected adverse reactions in accordance with the respective policies and procedures of the IRBs.

All Investigators (i.e., study site principal investigators) will also be promptly notified of these adverse events.

3. Other adverse events (eg, unexpected related adverse events of lesser severity or expected adverse events of any severity): These events will be reported in aggregate form to the DCC, overall study PI, and the DSMB at the time of regular data reports. However, sites will have the option of bringing any event to the immediate attention of the Study PI and DCC (via faxing the interim event report form) for review and discussion by the Steering Committee and for consideration of immediate reporting to the Head of the DSMB. Similarly, the DCC will have the option of bringing any event to the attention of the Steering Committee.

Sites will also follow and comply with their own local institution's adverse event reporting requirements. Depending on the local requirements, a site may report events locally that are not reported to the DCC.

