2.6 STUDY PROCEDURES AND MEASURES

Scheduling. The initial pre-treatment laboratory evaluations (conventional autoantibodies, viral studies, CBC with differential and platelets, pulmonary function tests-see Table 1 and Appendix A), if not otherwise clinically indicated, will be performed after informed consent is obtained, but within the subsequent two-week interval (maximum) prior to randomization and first treatment. Chest CTs must be obtained within 30 days prior to randomization and first study treatment. The conventional autoantibodies (ANA, RF, etc.), viral studies, and initial C3, C4, will be performed in the clinical lab of UAB. The CBC (with differential counts and platelets), and pulmonary function tests will be performed locally at each collaborating center and repeated at 1, 3, 6, and 9 months after treatment. These are standard of care tests for IPF patients. Screening and baseline studies can be performed concurrently or over the course of several days, if medically necessary or in best interests of subjects, as long as these studies are performed within the 14 day interval prior to first study treatment (or 30 days for CT scans).

Other routine clinical care for IPF patients will be followed as ordered by the primary physician.

Experimental immunologic studies for research purposes (experimental autoantibodies, lymphocyte phenotypes and mediators, longitudinal C3 and C4) will also be drawn after randomization, but within the 14 day period prior to the first treatment, and at 1, 3, 6, and 9 months after first treatments. These experimental tests will be performed using specimens shipped to UAB.

Following completion of screening assessments and determination of eligibility, the initial experimental treatment will be scheduled for a date within the next 14 days (allowing time for anti-HEp-2 autoantibody specimen processing, shipping to the central laboratory, and performing these assays). Computer-based randomization will occur on the day of initial treatment.

Subsequent study events will be scheduled relative to the date of randomization.

The second treatment will be scheduled for 14 days post-randomization, +/- two days. A window of +/- five days will be allowed in scheduling the 1-month assessment post-randomization, and a +/- seven-day window is allowed for subsequent evaluations at 3, 6, and 9 months post-randomization.

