The mechanisms responsible for beneficial clinical effects of rituximab are complex and incompletely understood, but include elimination of autoantigen-reactive CD20⁺ memory cells (plasma cell precursors), as well as alterations of B-cell antigen presentation, or B-cell costimulatory and/or chemotactic functions. Rituximab obviates or reduces deleterious effects of pathogenic autoantibodies. It has been used in thousands of patients over many years, and has a well-characterized and acceptable safety profile, unlike other much more experimental anti-B-cell agents (e.g., alemtuzumab, bortezomib, etc.). These other treatments are less specific, more toxic, and have only rarely been used in autoimmune patients. Their safety and efficacy for therapy of autoantibody diseases are unknown.

Reported serious adverse events (AE) following rituximab treatment include fatal transfusion reactions, although these seem to occur primarily in lymphoma patients and may be indistinguishable or overlap with tumor lysis syndrome (29-39,42) Serious transfusion reactions to rituximab have occurred in <1% of RA patients. Reactions occurring in >5% of these subjects were nausea (8%), hypertension (8%), upper respiratory tract infections (7%), and arthralgia (6%). Corresponding event rates in placebo controls were: 5%,5%,6%, and 4%, respectively. Uncommon or rare events include mucocutaneous reactions, progressive multifocal leukoencephalopathy, hepatitis B reactivations, and rare infections (29-39,42).

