5.1.2 Potential Risks of Experimental Interventions

The risks of steroid (methylprednisolone) (used as a premedication):

Common: insomnia, nausea, vomiting, or stomach upset; fatigue or dizziness; muscle weakness or joint pain; problems with diabetes control; or increased hunger or thirst.

Rare: acne, increased hair growth, thinning of the skin, cataracts, glaucoma, osteoporosis, roundness of the face, and changes in behavior

The risks of acetaminophen (Tylenol) (used as a premedication):

Uncommon risks include liver or kidney toxicities. In the doses used here these risks are rare.

The risks of diphenhydramine (Benadryl) (used as a premedication):

Common risks are drowsiness. Other, less common risks include dry mouth, urinary retention, cardiac rhythm disturbances, confusion.

The risks of Rituximab:

Common Risks: Fever, chills, headache, pain, rash, pruritus, angioedema, nausea, abdominal pain, cytopenias, weakness, cough, rhinitis. Infusion related reactions: angioedema, bronchospasm, chills, dizziness, fever, headache, hyper-/hypotension, myalgia, nausea, pruritus, rash, rigors, urticaria, and vomiting.

Infrequent Risks: Hypotension, peripheral edema, hypertension, flushing, edema, dizziness, anxiety, agitation, depression, hypoesthesia, insomnia, malaise, nervousness, neuritis, somnolence, vertigo, migraine, urticaria, hyperglycemia, hypoglycemia, hypercholesterolemia, diarrhea, vomiting, dyspepsia, anorexia, weight loss, anemia, pain at the injection site, back pain, myalgia, arthralgia, paresthesia, arthritis, hyperkinesia, hypertonia, neuropathy, conjunctivitis, lacrimation disorder, throat irritation, bronchospasm, dyspnea, upper respiratory tract infection, sinusitis, LDH increased.

Other Risks: Rare events associated with rituximab include severe mucocutaneous reactions, progressive multifocal leukoencephalopathy due to LC virus reactivation, hepatitis B reactivations, and other infections.

The risks of placebo:

Placebo contains no active medication. It is unlikely to be associated with any side effects.

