5.4. DATA SAFETY MONITORING PLAN

5.4.2 Data Safety Monitoring

A *Network* Data and Safety Monitoring Board (DSMB) independent of the study investigators will monitor this clinical trial for the duration of this proposal. The DSMB consists of experts in the field: Drs. [name] (U. Louisville) (chairman), [name] (U. Minn), [name] (Wash U.) and [name] (U. Texas Medical Branch).

The DSMB will be expected to convene as needed, but not less than every six months to review the progression of the study including patient enrollment, protocol compliance, and adverse event reports. The DSMB will conduct interim monitoring of accumulating data from research activities to assure the continued safety of human subjects, relevance and appropriateness of the study, and the integrity of research data.

The Food and Drug Administration (FDA) has exempted this clinical trial from IND regulations [21 CRF 312.2(b)] in recent correspondence (PIND 119573).

Each collaborating site will obtain local IRB approval prior to their enrollment of subjects.

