5.4.5 Frequency of Monitoring

The principal investigator will review subject safety data as it generated. The principal investigator, co-principle investigators, and the research staff will communicate by conference calls or visits at monthly interval to re-evaluate study goals, subject recruitment, data coding and retention, documentation and identification of adverse events, complaints and confidentiality of subjects. There will be an evaluation of the progress of the research study, including assessments of data quality, time lines, participant recruitment, accrual, and retention. The principal investigator will also review the outcome and adverse event data to determine whether there is any change to the anticipated benefit-to-risk ratio of study participation and whether the study should continue as originally designed or should it be re-evaluated and changed.

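### Section 5.4.7 guarantees the DSMB no prompt notice of a fatal or life-threatening suspected reaction that is judged expected

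*Combined protocol and SAP*

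**What the plan says.** Section 5.4.7 sets three routes for a site to report an event.

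- **Item 1:** serious and unexpected suspected reactions go to the DCC and the PI as soon as possible, with a 15-calendar-day limit. The DSMB is told promptly, with no number of days.
- **Item 2:** unexpected suspected reactions that are fatal or life-threatening go to the DCC, the PI and the DSMB within 2 working days.
- **Item 3:** all other events wait for the next routine data report, among them "expected adverse events of any severity): These events will be reported in aggregate form to the DCC, overall study PI, and the DSMB". Item 3 adds that "sites will have the option of bringing any event to the immediate attention of the Study PI and DCC", after which the Steering Committee may consider telling the head of the DSMB. The DCC may also raise an event with the Steering Committee.

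Under section 5.4.2 the DSMB is to "convene as needed, but not less than every six months". The stopping-rule text in 5.4.3.3 bases the study-wide rule on SAE rates by arm and gives the decision to the DSMB and NIH.

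On known harms, section 3.4 states "Reported serious adverse events (AE) following rituximab treatment include fatal transfusion reactions". Section 5.1.2 lists severe mucocutaneous reactions, progressive multifocal leukoencephalopathy, "hepatitis B reactivations, and other infections" among the rare rituximab risks.

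**The concern.** Sorting reports by expectedness is common for regulatory clocks. Here the same test also decides what the trial's own safety board is told quickly. The better an event is recognised as a rituximab harm, the weaker its claim to a fast report, even when it is fatal.

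The bodies that can stop the study are the ones affected. Their rule compares SAE rates between arms, and neither that rule nor the SAE definition in 5.4.6 sets expected events aside. Section 5.5.2 also names ongoing DSMB monitoring as a protection against the risks of the drug. A board that first learns of an expected fatal reaction from an aggregate table cannot act on it in the meantime, while further subjects are enrolled and infused.

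**Working it through.** The plan gives no figure of its own on this point, so the check is a comparison of texts followed by simple exposure arithmetic.

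**Step 1. Trace a fatal suspected reaction judged expected through every reporting route.**

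| Route | Applies if expected? | Reaches DSMB or NIH? | Deadline |
|---|---|---|---|
| 5.4.7 item 1 | No | DSMB, promptly | 15 calendar days to DCC and PI |
| 5.4.7 item 2 | No | DSMB | 2 working days |
| 5.4.7 item 3, main rule | Yes | DSMB, in aggregate | Next regular data report |
| 5.4.7 item 3, escalation | Yes | Head of DSMB, if the Steering Committee so decides | Optional, none stated |
| 5.4.3.3, SAE copies | Yes | No: local IRB and Coordinating Center | None stated |
| 5.4.3.1, SAE reports to Protocol Chair | Yes | No: the Protocol Chair is the PI. SAE safety reports are also distributed, with no recipient named | Described as timely, no number |
| 5.4.3.3, written summary | No: serious, unexpected and treatment-related events | DSMB and IRB | None stated |
| 5.4.5, PI review and monthly calls | Yes | No | Ongoing |
| 5.4.8, fatal or life-threatening reactions | No | NHLBI | 7 calendar days |

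One route carries such an event to the DSMB as a requirement: the aggregate report. Every route with a number of days attached requires the event to be unexpected. The 30-day NHLBI report of unanticipated problems in 5.4.8 does not change this, because it concerns risk greater than was previously known.

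**Step 2. Which events are expected?** No section defines the term or names a reference list. Sections 3.4 and 5.1.2 describe known risks but are not designated as that list.

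**Step 3. Exposure between DSMB reviews.**

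Inputs: Table 3 in section 2.11 gives 15 enrollments in a full year, and 58 subjects from 2/2014 to 11/2017 (45 months). Allocation is 1:1. The longest gap between DSMB meetings is six months (5.4.2). Assumptions: regular data reports follow that minimum schedule, and nobody escalates.

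- Full-year rate: 15 × 0.5 = 7.5 subjects; half on rituximab, 7.5 / 2 = 3.75.
- Even accrual over 45 months: 58 / 45 × 6 = 7.7 subjects; 7.7 / 2 = 3.9 on rituximab.
- First six enrolling months: 5 subjects, 2.5 on rituximab.
- Last six enrolling months: 15 × 0.25 + 8 = 11.75 subjects; 5.9 on rituximab.

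The central figure is therefore 7 to 8 subjects, about 4 of them on rituximab, and the range over Table 3 is 5 to about 12 subjects. If reports came every three months, the full-year figure would halve to 15 × 0.25 = 3.75 subjects, about 1.9 on rituximab.

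**The case against.** The strongest reply is that the plan has more safety traffic than 5.4.7 alone shows. Sites send individual SAE reports to the Coordinating Center whether or not the event was expected, and these pass to the PI. Section 5.4.5 adds that "The principal investigator will review subject safety data as it generated". Any event can be escalated at once, and the DSMB may meet whenever needed. All of this stands. A reader might infer from item 3 that an expected death is seen by everyone only in aggregate. The documents do not support that for the PI and the Coordinating Center. What remains is that these channels carry no deadline and none of them must end at the DSMB or NIH.

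A second reply concerns expectedness. A reader might infer that the named rituximab risks certainly miss expedited review. That is not established. Section 3.4 says that fatal reactions occur mainly in patients with lymphoma and that serious ones occurred in under 1% of rheumatoid arthritis patients. A site could reasonably call a fatal reaction in an IPF subject unexpected and use item 2. Another site could decide the opposite on the same text.

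A reader might also set the item 1 limit, "no later than 15 calendar days after the site Investigator receives the respective information", against the dosing schedule, "The second treatment will be scheduled for 14 days post-randomization, +/- two days", and infer that the clock outlasts the interval between infusions. This does not hold as a defect:

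- The difference is 15 − 14 = 1 day at the nominal interval, 15 − 12 = 3 at the short end and 15 − 16 = −1 at the long end.
- With the first infusion on Day 1, the latest second infusion falls on Day 1 + 16 = Day 17. A reaction known on Day 2 must be reported by Day 2 + 15 = Day 17, which is a tie.
- The limit follows an instruction to report as soon as possible, and it does not cover fatal or life-threatening reactions.
- Whether a subject continues treatment falls under the subject-level stopping rules in 5.4.3.3, which leave discretion to the investigator and do not depend on the reporting clock.

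Nor does that limit contradict 5.4.5: ongoing review by the PI and an outer limit for site submission can coexist.

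**Conclusion.** The point holds in a limited form. Section 5.4.7 sets no mandatory expedited report to the DSMB for a fatal or life-threatening suspected reaction judged expected, and no other section supplies one for the DSMB or NIH. This follows from the text and needs no assumption.

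The practical size is conditional. It requires a site to treat a known rituximab harm as expected, no use of the escalation option, no DSMB meeting before the six-month limit, and data reports on that same schedule. Under those conditions 7 to 8 subjects, about 4 on rituximab, could be enrolled before the board sees the event. The undefined term adds a further weakness, since sites may classify the same event differently. The gap does not affect the validity of the efficacy analysis. It is a shortfall in safety oversight that should be corrected because correction is cheap.

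**What to change.** Three wording changes:

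1. In item 2 of 5.4.7, delete the word unexpected, so that every fatal or life-threatening suspected reaction goes to the DCC, the PI and the DSMB within the existing 2 working days. Keep the word suspected, so that deaths from IPF not attributed to study drug stay outside this route.
2. In item 3, exclude fatal and life-threatening suspected reactions from aggregate reporting.
3. Reconcile 5.4.7 with the SAE routing in 5.4.3.1 and 5.4.3.3, including the written summary to the DSMB, which applies the same expectedness filter.

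The NHLBI clock in 5.4.8 can keep its test of unexpectedness. Because item 1 and 5.4.8 would still use that test, the protocol should also name the document that decides it.

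The cost is a small number of extra single-event reports on the interim event report form already mentioned in 5.4.7. A rough ceiling for the fatal ones comes from the median survival of about 3 years in section 1.3. With exponential survival, 1 − 0.5^(0.75/3) = 16% would die within nine months, and 0.16 × 58 is about 9 deaths in the whole trial. Only deaths judged suspected reactions would need the report. Life-threatening events would add to this, and the documents give no rate for them.

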5.4.8. Reporting Adverse Events (AE) and Unanticipated Problems (UP) to NHLBI

Unexpected, life-threatening or fatal suspected adverse reactions will be reported to the NHLBI within 7 calendar days. Unanticipated problems suggesting greater risk of harm to study participants than was previously known or recognized will be reported to NHLBI within 30 calendar days. Expedited SAE/UP reports to NHLBI will include the following elements:

- Study title, grant/contract number, PI name
- Description and date of the event or problem, including why it merits expedited reporting

- When available, date(s) when the event was reported to applicable governing bodies (e.g., IRB)
- Any corrective action planned or taken in response to the event or problem (e.g., study suspension, consent or protocol changes, additional training or security measures)

Communications from other applicable oversight bodies (eg: IRBs, DSMB) regarding any applicable SAE/UP will also be reported to NHLBI.

5.5 RISK MANAGEMENT PROCEDURES

5.5.1 Protection Against Risks

General Risks of Study Protocol and Procedures

All research interventions/activities will be conducted in private patient care areas. The collection of sensitive information about subjects is limited to the amount necessary to achieve the aims of the research, so that no unneeded sensitive information is being collected.

To avoid any violation of subject confidentiality, all data will be stored in a password-protected database, identified only by study ID number at the DCC. A confidential database linking patient identifying information with study ID number will be maintained at each clinical site.

All demographic and clinical information about the subject will be stored on an electronic password-guarded study database under the supervision of the PIs for this protocol. All staff will sign confidentiality statements. Access to the database will be limited to the data manager and staff under the supervision of the PIs.

Specimens will be stripped of subject identifiers and stored according to a similar coding protocol as described above. These specimens will be stored safely in the custody of the PI responsible for the individual assays. The Investigators will limit future access to any remaining sample to only those investigators with prior IRB approval for their studies.

All staff involved in this study are properly credentialed and instructed in the areas of testing, confidentiality, and safety.

The PIs will retain the data for the entire period of this study. The investigators may continue to use and disclose subjects de-identified information for the purpose of this study for a minimum of seven years after final reporting or publication of the study. If the subject and/or legal representative decide to withdraw or be withdrawn from study participation, they may request that the study data and samples be destroyed.

5.5.2 Protection Against Potential Risks of Experimental Intervention

Despite the documented safety profile of rituximab in other human disorders of abnormal immune regulation, the study has been designed with a focus on protecting patients against risk including:

Selection of a target patient population with a very high risk of morbidity and mortality due to the absence of a defined treatment for the disorder

Involvement by trained staff / investigators with experience in the administration of Rituximab

Prior human experience with the study medication in similar conditions with an autoimmune hypothesis including rheumatoid arthritis and myositis

Exclusion of all patients with conditions which might simulate IPF such as congestive heart failure, pneumonia, and pulmonary thromboembolism

Continuous monitoring by an independent DSMB

Rituximab:

The patient population will receive pre-treatment with oral acetaminophen, oral diphenhydramine, and methylprednisolone (100mg IV) prior to drug administration. Based upon the experience of the study investigators to date, and published reports, this regimen will significantly lessen the risk of general reactions to the medication.

Required Education in the Protection of Human Research Participants

All investigators and study personnel involved in the conduct or oversight of human participant research are required to complete initial and continuing education in the protection of human research participants.

